## Outcome Measures

### Primary Endpoint: Falls

In this study, a fall is defined as unintentionally coming to rest on the ground or at some other lower level, not as a result of a major intrinsic event (e.g., stroke or syncope) or overwhelming hazard [13]. Falls over one year prior to baseline will be ascertained to characterize the sample and check for equality of randomization. Prospective assessment of falls will be done using the current gold standard of collecting monthly reports [45] returned by postal and/or electronic mail, an efficient (1-2 minute completion time) and effective method used by our team and others [41, 46-48]. In two prior studies we obtained 98% of monthly fall reports over 6 months [46, 49]. Participants will be provided with a monthly falls calendar to record falls when they occur, in order to reduce issues of recall and false negatives. Each participant that records a fall will be phoned to confirm that each fall meets the standard definition in order to reduce the risk of false positives, and to obtain information about the fall (e.g., how it occurred) and any resultant injury. An “injurious” fall is one that results in fractures, head injuries, sprains, bruises, scrapes, or serious joint injuries, or where the participant seeks medical care [13]. Of primary interest in the proposed study is the # of falls, with the # of injurious falls and medical care resulting from a fall being used for descriptive purposes of the study population.

Secondary Endpoint: Frailty will be measured using the components of the Frailty Phenotype [29]. The original 5 criteria of the phenotype (shrinking, exhaustion, low activity, slowness, and weakness) were limited to the measures available in the Cardiovascular Health Study [29]. The phenotype can now be measured more accurately with objective measures (e.g., lean body mass rather than self-report weight loss[50]). In this study, we will assess each frailty component using measures that will most accurately capture frailty criteria in the prostate cancer survivor population and where cutoff scores can be appropriately determined. A total frailty score will be calculated in the same manner as that of Fried:  $\geq 3$  criteria = frail; 1-2 criteria = prefrail; 0 criteria = robust. Since each variable is a continuous measure we will examine changes in each individual frailty component to determine how each intervention may shift frailty among our sample. Criteria are measured as follows:

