## 13.0 BIO-STATISTICAL CONSIDERATIONS

### Power and Sample Size

We have powered the sample size based on our primary aim. In older adults, 20%-30% of community-dwelling elders are likely to fall within 1 year [11] and Li and others have reported a reduction in fall risk of 47% from 3 [86] or 6 [41] months of tai ji quan exercise. We are using an effect size for tai ji quan to power for both interventions because we have these data available from our prior work and effects sizes for strength training are similar to tai ji quan [87]. Our study will determine if strength training is as effective as tai ji quan. Using PASS 2008[88], based on a negative binomial regression model [89], at alpha = .05, the variance shared among the dummy vectors representing treatment ( $R^2=.25$ ), and an estimate of the overdispersion parameter (Phi) of 2.5, a sample size of n=300 (n=100 per group) participants will provide 80% power to detect at least a 47% reduction in the fall incidence rate over six months by being in either of the 2 exercise groups versus control. To protect against an estimated attrition of ~17% during the intervention period, 120 participants will be randomized per group (total sample size: N=360). The attrition estimate is conservatively based on the highest attrition rate from our prior strength training trials in prostate cancer survivors (0% and 16% attrition in 6 and 12 month trials, respectively [37, 39]). Though the total # of falls is the primary endpoint, the sample size of N=300 also provides sufficient power to detect differences between experimental and control groups on secondary outcomes of frailty and physical function. We and others' have data on the effect of exercise on individual components of frailty in prostate cancer survivors on ADT and self-report physical function. With a sample of N=100 per group we have a sufficient sample to detect a difference in 2.5% of lean body mass [90, 91], a 4 sec. faster chair stand time [37, 91], a 1.1 sec. faster gait speed [91], and a 9% difference in self-report physical function scores [37].

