Aim 1: Compare the relative efficacy of tai ji quan and strength training to prevent falls: We will determine the efficacy of tai ji quan and strength training by comparing each of them to the control condition while adjusting for important covariates using negative binomial regression models which will analyze total number of falls per participant that occur from baseline to 6 months. A negative binomial regression was chosen over a Poisson regression for modeling the count data because of the overdispersion that is common with actual research data. [88, 93] Intervention type will be entered into the model as 2 dummy variables, with the reference group being the control group. This will allow a comparison of the each of the intervention groups against control. A *second* model will be run with strength training as the reference category to compare the intervention groups to each other. In addition to standard ITT analysis, the impact of participants who drop out of the study on the falls outcome will be examined in a secondary data analysis. A significant incidence rate ratio (IRR) less than 1.0 for the dummy vector representing tai ji quan and/or strength training would provide support for the hypothesis that the respective intervention reduced the rate of falls compared to the control group.

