### **Additional Analyses**

Injurious falls: Though the proposed study is not powered to examine reductions in injurious falls from the intervention, we will conduct an additional analysis on this important outcome. An injurious fall is one that results in fractures, head injuries, sprains, or serious joint injuries, or in a participant seeking outside medical attention. We will conduct this analysis among the subsample that had at least 1 fall using logistic regression.

Mechanisms of intervention effects on falls: We can use strength and stability measures to identify the mechanism(s) by which each exercise approach may reduce falls, strengthening support for exercise as a fall prevention strategy. We will test 3 mediators, muscle strength (chair stand time) and stability (walk speed and postural sway) as possible mediators because both measures may be affected by each intervention and each possible mediator is a major risk factor for falls. Mediation of the intervention effect by changes in performance measures will be analyzed using Mplus. A manifest model will be tested with the dummy vectors representing tai ji quan and strength training as exogenous variables, change in strength and as endogenous variables (mediators), and number of falls over the intervention period as an endogenous variable (outcome). Significant indirect parameter estimates based on standard errors using the multivariate delta method from the treatment variables to number of falls through changes in strength and stability would provide support for mediation.

Potential moderators of sustained exercise after the intervention: Linear and logistic regression models will be used to explore different predictors (e.g., age, comorbidities, timing of ADT, etc.) of adherence to exercise after structured training stops.

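### Injurious falls are collected as a count but analysed yes/no by logistic regression among fallers only; a count model in all randomised men would use the data better, at a gain that depends on unstated rates

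*Combined protocol and SAP*

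**What the plan says.** Section 3.0 (Primary Endpoint: Falls) sets up the ascertainment: "Each participant that records a fall will be phoned to confirm that each fall meets the standard definition". The same call records how the fall occurred and any injury. The number of injurious falls is therefore held for each man, but that section gives it a limited role, "with the # of injurious falls and medical care resulting from a fall being used for descriptive purposes of the study population".

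Section 13.0 (Additional Analyses, Injurious falls) then plans an inferential analysis. It opens with a caveat, "Though the proposed study is not powered to examine reductions in injurious falls from the intervention", calls the outcome important, and specifies: "We will conduct this analysis among the subsample that had at least 1 fall using logistic regression". The coding of the outcome is not spelled out. Logistic regression in a subsample of men implies any versus no injurious fall per man.

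For all falls, Aim 1 in section 13.0 uses "negative binomial regression models which will analyze total number of falls per participant that occur from baseline to 6 months", chosen because such counts are overdispersed.

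The two sections define an injurious fall differently. Section 3.0 includes bruises and scrapes; section 13.0 does not.

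**The concern.** Injurious falls are a subset of the events that Aim 1 counts, and the plan gives no reason for putting them on a coarser scale. A man with one injurious fall and a man with several score the same, so a reduction in repeat injuries within a man cannot show. The result is an odds ratio, which cannot be compared with the primary rate ratio to see whether injurious falls decline in proportion to all falls.

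The analysis set adds a second problem. Having at least one fall is itself an outcome that exercise is meant to change. Restricting to fallers asks whether men who fell were injured, not whether exercise reduced injurious falls, and it breaks the randomised comparison.

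**Working it through.** **Inputs from section 13.0 (Power and Sample Size).** 100 men per group and 80% power ("a sample size of n=300 (n=100 per group) participants will provide 80% power"); rate ratio 0.53 ("at least a 47% reduction in the fall incidence rate over six months"); alpha 0.05, taken as two-sided ("based on a negative binomial regression model [89], at alpha = .05"); Phi 2.5; R² 0.25.

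**Not given, so assumed.** Control falls per man in 6 months (μ), the share of falls that injure (q, 10-70%), and that the full 47% reduction carries over to injurious falls.

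**1. The plan's own figure.** The overdispersed Poisson-regression formula is N = Phi × (1.960√V0 + 0.842√V1)² / (μ × (ln 0.53)² × (1 − R²)), with V0 = 1/[p(1−p)] and V1 = 1/(1−p) + 1/(0.53p), where p is the proportion coded 1 on the arm dummy.
- p = 1/3: V0 = 4.5, V1 = 7.16, squared term 41.09. So N = 2.5 × 41.09 / (μ × 0.403 × 0.75) = 339.8/μ, and N = 300 needs μ = 1.13.
- p = 1/2: N = 292.0/μ, so μ = 0.97.
- Entering 0.2-0.3 falls with p = 1/3 gives N = 1,699 to 1,133.

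The stated power therefore implies about 1 fall per man in 6 months. The only frequency printed is that 20-30% of older adults in general fall in a year.

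**2. Count model, all men.** Read Phi as variance/mean, so k = 1.5/μ = 1.33 at μ = 1.13. With m0 = μq and m1 = 0.53μq, SE(log rate ratio) = √[(1/m0 + 1/m1 + 2k)/100].
- All falls (q = 1): √[(0.885 + 1.670 + 2.655)/100] = 0.228; z = 0.635/0.228 = 2.78; power 79.4%, in line with the stated 80%.
- q = 0.5: √[(1.770 + 3.339 + 2.655)/100] = 0.279; z = 2.28; power 62.5%.

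**3. Yes/no model, all men.** P(any) = 1 − (1 + km)^(−1/k). At q = 0.5 this is 34.4% in control and 22.3% with exercise. The log odds ratio is 0.604, SE 0.319, power 47.2%. The loss is 62.5 − 47.2 = 15.3 points.

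**4. Range of the loss from the scale alone (points, all men).**

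| Injurious share | Formula, μ = 1.13 | Simulation, μ = 0.97-1.13, Phi read as variance/mean or as k |
|---|---|---|
| 10% | 1.5 | 0.7-3.0 |
| 20% | 4.8 | 5.1-8.0 |
| 30% | 8.5 | 8.5-11.6 |
| 50% | 15.3 | 13.7-18.1 |
| 70% | 20.7 | 20.6-21.5 |

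At μ = 0.2-0.3 the formula gives 0.2 to 6.0 points over the same shares. Simulations set to 20-30% fallers per year, with 30-50% of falls injurious, gave −0.5 to 3.9. The formula never favours yes/no; in the simulations yes/no was ahead by less than 1 point, and only at low rates.

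**5. The fallers-only restriction.** At μ = 1.13 and q = 0.5, 49.9% of control men and 35.6% of exercise men fall. Among fallers, the proportion with any injurious fall is 34.4/49.9 = 69% against 22.3/35.6 = 63%. The men whose falls were prevented have left the comparison, and most of the effect has gone with them. Simulated power in this setting is 63.4% for the count in all men, 46.8% for yes/no in all men and 9.8% for yes/no in fallers. The scale costs 16.6 points and the restriction a further 37.0. Across μ = 0.97-1.13 and q = 10-70%, the planned analysis has about 5-10% power if exercise reduces falls but not injuries per fall.

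**The case against.** This is an additional analysis, openly declared unpowered, of an outcome that section 3.0 treats as descriptive. The proportion of men with any injurious fall is a legitimate and readable summary. Men with many injurious falls are rare: at 1.13 falls and a 50% share, under 1% of control men would have five or more, though about 13% would have two or more. The calculations also favour the count model, since the data are generated as negative binomial, the full 47% effect is carried over, and sensitivity to a few frequent fallers was not tested. If exercise also cut the share of falls that injure by 30% (from an assumed 40%, at 1.13 falls), the planned analysis would have 44% power, against 88% for the count in all men. These points limit the importance of the concern. They give no reason to discard a count already in hand.

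A reader might infer a fixed loss of roughly 9 to 20 points. The documents do not support that. It needs about 1 fall per man in 6 months, which is solved back from the stated power, and a 30-70% injurious share, which appears nowhere. The narrower definition in section 13.0 makes a lower share plausible. Equally, the 20-30% yearly figure describes older adults in general, whereas this trial selects men with a recent fall or slow performance tests, so the low end is not established either.

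A reader might also infer that the scale costs power whichever men are analysed. Within fallers, the simulated difference between count and yes/no ran from about −3 to +25 points, so that does not hold throughout.

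**Conclusion.** The concern holds in a limited form. The plan collects the number of injurious falls and does not use it for inference; its yes/no model cannot register repeat injuries and does not line up with the primary rate ratio. The power cost of the scale alone is 0 to 22 points, conditional on an unstated fall rate and injurious share, and towards the upper part of that range only if the rate is the one implied by the plan's own power statement. The fallers-only restriction is the larger fault in the scenarios consistent with the stated power.

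It would go too far to call this the trial's most clinically important fall outcome. The plan calls it important, makes the number of falls primary, and already captures recurrent falls of all kinds through Aim 1. Neither the primary analysis nor the sample size is affected. Importance is minor to moderate.

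**What to change.** In section 13.0 (Additional Analyses, Injurious falls), replace the logistic regression sentence with:

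> The number of injurious falls per man from baseline to 6 months will be analysed in all randomised men (0 for men with no injurious fall) with the Aim 1 negative binomial model (same arm dummies and covariates, with log months of fall reporting as offset), reporting incidence rate ratios; the proportion of men with any injurious fall will be reported by arm descriptively.

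The population and the offset must be written out, because Aim 1 as printed has no rule for follow-up time. In the same edit, use one definition of injurious fall in sections 3.0 and 13.0, since bruises and scrapes change the share that drives the result, and amend the descriptive-only wording in section 3.0.

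The cost is a few lines of text and the reuse of an existing model, with no new data. Sparse counts or a few frequent fallers may call for a robust standard error or a sensitivity check. The analysis stays exploratory and unpowered, and should still be labelled so.

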5. *Weakness*: In contrast to grip strength used by Fried in her original phenotype, lower body strength is more closely linked to falls, mobility, and dysfunction and can be easily obtained using well established timed chair stand test (seconds required to rise from chair 5 times)[68, 69]. Chair stand time  $\geq 12$  seconds has been shown to predict a 2.4 increased risk of falls in older adults and we will apply this cutoff for "weakness"[70].

We will also assess frailty at baseline using the FRAIL scale self-report measure, as we have done in our previous study [8].

Secondary Endpoint: Physical Function: Physical function will be measured objectively (mobility, balance) and subjectively (perceived function by self-report).

*Functional Mobility*: The Timed Up and Go (TUG) test is a reliable [71] and widely accepted clinical measure of mobility that evaluates the time that it takes a person to rise from a chair, walk 7 m, turn around a cone and return and sit in the chair [72]. Slower TUG times are associated with an increased risk of falls [73] and disability [69]. [name], a Co-Investigator, developed an instrumented version of the TUG test that incorporates wearable sensors to detect changes in mobility that are not apparent from the stopwatch TUG score.[74] The iTUG system can electronically capture individual elements of the TUG test at a very sensitive level to detect small changes over time and decrements in higher functioning patients that might be missed by a stopwatch time. TUG time is our main outcome, but we will examine additional information provided by the iTUG (e.g., segment time, step #) to understand which components of mobility ADT affects. A 7-meter dual task will also be conducted. A participant will be asked to count

backwards by 3's starting at 99. In addition, standing balance tests will be done as part of the Physical Performance Battery.

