All analyses will retain each participant in the group he was randomly assigned regardless of missing data or drop out status (i.e., intention to treat). We will track medical treatment changes and disease progression during the study to describe the sample or justify why participants exited the study. In the unlikely event of a large subgroup, these data could be used for exploratory subgroup analysis to suggest directions for future research. Age, timing of ADT (current vs. past), fall history at enrollment and baseline frailty will be considered as possible covariates in all analyses. Age and timing of ADT (past vs current) are included since they may affect exercise tolerance and/or responsiveness to exercise training; fall history is included because we want to examine the efficacy of the interventions to reduce falls in men with a fall history and prevent falls

among men who have not recently fallen. Analyses will be conducted in Stata, R, and/or Mplus statistical software packages. Full information maximum likelihood estimation (FIMLE) will be used to estimate the models, as appropriate, because it is less biased and more efficient than other techniques for handling missing or incomplete data[92].

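### The falls mediation model uses raw change scores without the mediators' baseline values, which can bias the performance-to-falls path and hence the indirect effect

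*Combined protocol and SAP*

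**What the plan says.** The paragraph on mechanisms in section 13.0, Additional Analyses, names the candidates: "We will test 3 mediators, muscle strength (chair stand time) and stability (walk speed and postural sway) as possible mediators". It fixes their form: "Mediation of the intervention effect by changes in performance measures will be analyzed using Mplus". It then describes the model: "A manifest model will be tested with the dummy vectors representing tai ji quan and strength training as exogenous variables", with "change in strength and as endogenous variables (mediators), and number of falls over the intervention period as an endogenous variable (outcome". A word seems to be missing after strength; from the sentence before it, stability is presumably meant. The test is specified as "Significant indirect parameter estimates based on standard errors using the multivariate delta method".

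The paragraph mentions no baseline value of a mediator, no residualised change and no model for the follow-up level. A general rule earlier in section 13.0 says: "Age, timing of ADT (current vs. past), fall history at enrollment and baseline frailty will be considered as possible covariates in all analyses". The baseline values of the three performance tests are not on that list. Under Aim 1, falls are counted as "total number of falls per participant that occur from baseline to 6 months", the same six months in which performance is meant to change.

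**The concern.** An indirect effect is the product of two paths. Randomisation protects the first, from arm to change in performance. It does not protect the second, from change in performance to falls, which is an observational association within arms.

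Baseline performance is an obvious confounder of that second path. Because repeat measurements correlate imperfectly, men who start slow or unsteady tend to show the larger improvement. By the protocol's own rationale they also fall more: section 3.0 justifies the chair stand cut-off and the sway measure by their ability to predict falls, which is a statement about level. With baseline left out, a large improvement partly stands for a poor start, and the benefit of improving is offset by the risk of having started badly.

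At stake is the purpose of this analysis, which is to show how each type of exercise might reduce falls. A biased second path can leave a real mechanism without support or, in less usual conditions, misstate its size or sign.

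**Working it through.** The documents give no power, effect size, SD or repeat correlation for this analysis, so there is no stated figure to reproduce.

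**1. Inputs.** From section 13.0: 100 men per arm analysed, overdispersion phi 2.5, alpha 0.05 (two-sided assumed). Assumed, because the documents do not give them: 0.5 control falls per six months, an arm effect of 0.4 SD on the mediator, pre-post correlation r of 0.5, 0.7 or 0.9, and a post/pre SD ratio s of 0.8, 1.0 or 1.2.

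**2. Formula.** Within arms let log fall rate = b1·pre + b2·post, with pre SD = 1. If only change = post − pre is entered, its coefficient is

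b* = [b1·Cov(pre, change) + b2·Cov(post, change)] / Var(change),

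where Cov(pre, change) = rs − 1, Cov(post, change) = s² − rs and Var(change) = 1 + s² − 2rs.

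**3. Equal variances (s = 1), b* as a share of b2.**
- Falls follow the follow-up level (b1 = 0): (1 − r)/[2(1 − r)] = 0.50 at any r.
- Falls follow the pre-post average (b1 = b2): [(r − 1) + (1 − r)]/[2(1 − r)] = 0.
- Half change, half level (b1 = −b2/2): 1.5(1 − r)/[2(1 − r)] = 0.75.
- Change alone (b1 = −b2): Var(change)/Var(change) = 1.00, no bias.

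**4. Unequal variances, follow-up-level case:** share = (s² − rs)/(1 + s² − 2rs).

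| r | s = 0.8 | s = 1.0 | s = 1.2 |
|---|---|---|---|
| 0.5 | 0.29 | 0.50 | 0.68 |
| 0.7 | 0.15 | 0.50 | 0.79 |
| 0.9 | −0.40 | 0.50 | 1.29 |

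For example, r = 0.9 and s = 0.8 give (0.64 − 0.72)/(1.64 − 1.44) = −0.08/0.20 = −0.40. The path can therefore reverse or be inflated.

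**5. With baseline in the model.** b1·pre + b2·post = (b1 + b2)·pre + b2·change. The coefficient on change is then b2 in every case, and the model is the same as one using the follow-up value with baseline as covariate.

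**6. Simulation.** 400 replicates per setting, s = 1, log-link count regression with robust standard errors, delta-method test of the indirect effect. Simulation error is up to √(0.25/400) = 2.5 percentage points. Three models were fitted: change only, change plus baseline, and change plus a dichotomised baseline as a stand-in for baseline frailty. Entries are for r = 0.5/0.7/0.9.

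| Falls follow | Model | Mean slope | Power, indirect effect (%) |
|---|---|---|---|
| Follow-up level (true 0.50) | change only | 0.25/0.26/0.25 | 20/18/12 |
| | + dichotomised | 0.38/0.40/0.40 | 44/43/27 |
| | + baseline | 0.50/0.51/0.50 | 60/61/39 |
| Average (true 0.25) | change only | 0.01/−0.01/0.02 | 2/2/5 |
| | + dichotomised | 0.15/0.13/0.17 | 9/7/11 |
| | + baseline | 0.27/0.24/0.27 | 27/14/14 |
| Change alone (true 0.50) | change only | 0.50/0.50/0.50 | 62/62/39 |
| | + baseline | 0.50/0.50/0.49 | 65/58/38 |

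**7. Entry rule.** Section 5.0 admits men with a fall in the past year or, failing that, a slow TUG or chair stand. This selects on baseline and makes the variances unequal. In simulations of such a rule (assumed r 0.6-0.8, illustrative cut-offs), change only gave 0.28-0.32 of 0.50 (56-64% kept) and 0.03-0.07 of 0.25. Adding fall history and a frailty-type cut gave 0.40-0.41 of 0.50 (80-82%) and 0.16 of 0.25 (64%). Adding the baseline value itself gave 0.50-0.51 and 0.24-0.26.

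**The case against.** The strongest reply is that the plan already offers some protection. The covariate rule in section 13.0 applies to all analyses and names age, fall history and baseline frailty. Frailty includes the chair stand and the walk, two of the three mediators. Together with the entry rule, these covariates recover about 80% of the slope in the follow-up-level case. This stands as mitigation but is not a cure. The covariates are only to be considered, frailty uses cut-offs rather than measured values, and sway is not one of its components.

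A reader might go further and infer that the model necessarily halves or cancels the mediator path. The documents do not support that. Both results need equal variances before and after and falls that depend on level, and no SD, correlation or driver of falls is stated. Elsewhere the bias is milder, absent, inflating or reversed.

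A reader might also infer that the trial would declare strength or stability irrelevant to falls. The plan sets no rule for concluding that mediation is absent. It says only what significant indirect estimates would support.

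Finally, the analysis is additional and unpowered, and even with baseline included the power is modest. This is true and limits the importance of the point.

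**Conclusion.** The point holds as a possible bias, usually attenuation, in an additional analysis. As written, the mediator-to-falls path is open to confounding by baseline performance, and the optional covariates close it only in part.

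The structural results (half, zero, no bias) are exact under their stated conditions. The average case is realistic here because falls are counted while performance is changing. The power figures are illustrations: they rest on the assumed base rate, arm effect and correlations in the working and on equal variances, and should not be read as predictions for this trial.

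Nothing material is lost if falls truly depend on change alone, since power then differs only within simulation error. Measurement error and other confounders of the second path would remain after the correction. The arm-to-mediator path and the primary falls comparison are unaffected.

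**What to change.** In the mechanisms paragraph of Additional Analyses, state that the baseline values of chair stand time, walk speed and postural sway enter as covariates in both the mediator equations and the falls equation. Using the follow-up values as mediators with baseline as covariate is equivalent. State also that fall history at enrolment and age are included in the falls equation, rather than only considered.

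The cost is a sentence or two of SAP wording. The Schedule of Events already has all three tests at baseline, 3 and 6 months. A change score cannot be formed without the baseline value, so no man is lost from the analysis.
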